10.7 Appendix 7: Country-specific Requirements

Not applicable.

10.8 Appendix 8: Abbreviations

Abbreviation	Expanded Term
AE	adverse event
APaT	all participants as treated
ANOVA	analysis of variance
CSR	Clinical Study Report
CDC	Centers for Disease Control and Prevention
ECG	electrocardiogram
ECL	electrochemiluminescence
eCRF	electronic Case Report Form
ELISA	enzyme-linked immunosorbent assay
EMA	European Medicines Agency
FAS	full analysis set
FDAAA	Food and Drug Administration Amendments Act
FBR	Future Biomedical Research
GCP	Good Clinical Practice
GMC	geometric mean concentration
GMT	geometric mean titer
IB	Investigator's Brochure
ICF	Informed Consent Form
ICH	International Conference on Harmonization
IEC	Independent Ethics Committee
IgG	immunoglobulin G
IPD	invasive pneumococcal disease
IRB	Institutional Review Board
MSD	Merck Sharp & Dohme Corp.
NIP	National Immunization Program
PCV	pneumococcal conjugate vaccine
PD	pneumococcal disease
PD3	post-Dose 3
PD4	post-Dose 4
PnECL	pneumococcal electrochemiluminescence
PnPs	pneumococcal polysaccharide
PP	Per-protocol
RNA	ribonucleic acid
SAE	serious adverse event
SoA	schedule of activities
SOC	system organ classes
sSAP	supplemental statistical analysis plan
VRC	Vaccination Report Card
WHO	World Health Organization

1 INTRODUCTION

This supplemental SAP (sSAP) is a companion document to the protocol. In addition to the information presented in the protocol SAP which provides the principal features of analyses for this trial, this supplemental SAP provides additional statistical analysis details/data derivations and documents modifications or additions to the analysis plan that are not “principal” in nature and result from information that was not available at the time of protocol finalization.

2 SUMMARY OF CHANGES

[15-Nov-2019]

Section 3.6.1 Statistical Methods for Immunogenicity Analyses

The following analyses have been added:

- Analyses of IgG (proportion of participants $\geq 0.35 \mu\text{g/mL}$ and GMC) in subjects with baseline IgG $< 0.35 \mu\text{g/mL}$.
- Reverse cumulative distribution curves

Appendix

Reference to the patient registration center has been removed, and the reference to the unblinded clinical scientist has been added.

3 ANALYTICAL AND METHODOLOGICAL DETAILS

3.1 Statistical Analysis Plan Summary

Key elements of the statistical analysis plan are summarized below; the comprehensive plan is provided in [Sections 3.2 – 3.12](#).

Trial Design Overview	A Phase I, Double-Blind, Randomized, Multicenter Trial of the Safety, Tolerability, and Immunogenicity of V114 in Healthy Japanese Infants
Treatment Assignment	This is a double-blind trial with three vaccination groups. Participants will be randomized to V114-subcutaneous (SC), V114-intramuscular (IM), and PCV13-SC in a 1:1:1 ratio.
Analysis Populations	Safety All Participants as Treated (APaT) Immunogenicity Primary: Per-protocol (PP)
Primary Endpoints	Solicited injection-site adverse events (AEs) (redness, swelling, hard lump, pain/tenderness) from Day 1 through Day 14 postvaccination Solicited systemic AEs (irritability, drowsiness, hives/welts, appetite loss) from Day 1 through Day 14 postvaccination Vaccine-related serious AEs (SAEs) from Day 1 through 1 month post-Dose 4 (PD4)
Secondary Endpoints	The following endpoints at 1 month post-Dose 3 (PD3): Anti-pneumococcal polysaccharide (PnPs) serotype-specific immunoglobulin G (IgG) response rates (proportion of participants meeting serotype-specific IgG threshold value of $\geq 0.35 \mu\text{g/mL}$) for the 15 serotypes contained in V114 IgG geometric mean concentrations (GMCs) for the 15 serotypes contained in V114 Proportion of participants meeting threshold values for diphtheria toxin, tetanus toxin, pertussis toxin, pertussis filamentous hemagglutinin (FHA) as well as polio virus types 1, 2 and 3.

Statistical Methods for Key Immunogenicity Analyses	
The proportion of participants with IgG concentrations $\geq 0.35 \mu\text{g/mL}$ at 1 month PD3 for the 15 serotypes contained in V114 will be summarized by vaccination group. Within-group 95% confidence intervals (CIs) will be calculated based on the method of Clopper and Pearson. The between-group differences, along with the corresponding 95% CIs based on the method of Miettinen and Nurminen [Miettinen O., et al 1985], will be calculated. The proportion of participants meeting threshold values at 1 month PD3 for diphtheria toxin, tetanus toxin, pertussis toxin, pertussis FHA as well as polio virus types 1, 2 and 3 will be analyzed in the same fashion.
 
The IgG concentrations at 1 month PD3 will be natural log transformed and analyzed using an analysis of variance (ANOVA) model with a single factor for vaccination group. The within-group means and the between-group mean differences, along with the corresponding 95% CIs, will be estimated using this model. The point estimates as well as the lower and upper limits of the 95% CIs will be exponentiated to obtain the estimates on the original scale for IgG GMCs by vaccination group and IgG GMC ratios.

Statistical Methods for Key Safety Analyses	
The analysis of safety results will follow a tiered approach. The tiers differ with respect to the analyses that will be performed.
 
Tier 1 safety endpoints include solicited injection-site AEs and solicited systemic AEs during Day 1 to Day 14 postvaccination that are specifically prompted for on the vaccination report card (VRC). Endpoints not defined as Tier 1 will be classified as belonging to "Tier 2" or "Tier 3". Tier 2 endpoints include AE summary measures (any AE, any vaccine-related AE, any SAE, any vaccine-related SAE, discontinuation of study vaccine due to an AE), AEs [specific terms as well as system organ classes (SOCs)] that occur in at least 4 subjects in any vaccination group, and axillary temperatures ($\geq 37.5^\circ\text{C}$, $\geq 38.0^\circ\text{C}$, $\geq 39.0^\circ\text{C}$, $\geq 40.0^\circ\text{C}$) collected from Day 1 through Day 7.
 
p-Values (for Tier 1 endpoints) and 95% CIs (for Tier 1 and Tier 2 endpoints) will be provided for between-group differences in the percentage of participants with events. These analyses will be performed using the Miettinen and Nurminen method.

Interim Analysis	An interim analysis will be performed after all participants continuing on the trial have completed the study visit at 1 month PD3 and the data (safety and immunogenicity) up to that point have become available. Group summaries of the results will be reviewed; however, the study team will remain blinded at the subject level. Only designated unblinded Sponsor personnel will review the safety data at the subject level, and will be responsible for communicating in a blinded manner to the blinded study team. The information noted above will be used to make scientific decisions regarding future studies. The conduct of this trial will not be altered by the interim analysis.
Multiplicity	Multiplicity adjustment is not planned.
Sample Size and Power	A total of 120 participants will be equally randomized, with 40 participants in each of the three vaccination groups. If the true incidence of a particular safety event is 4%, then there is 80% probability that the event is observed in at least one in 40 participants.

3.2 Responsibility for Analyses/In-house Blinding

The statistical analysis of the data obtained from this trial will be the responsibility of the Clinical Biostatistics department of the Sponsor.

This trial will be conducted as a double-blind trial under in-house blinding procedures. The Sponsor personnel, except those who are specifically designated to serve as unblinded roles (see Section 6.3.3 of the protocol, and Section 3.7), will remain blinded to the treatment assignment of individual participants until the end of the trial. Site personnel, except those who are specifically designated to serve as unblinded roles (see Section 6.3.3 of the protocol), as well as participants and their parents/legal guardians, will also remain blinded until the end of the trial.

The Clinical Biostatistics department will generate the randomized allocation schedule for trial treatment assignment. Randomization will be implemented using interactive response technology (IRT) or its equivalent.

The planned interim analysis is described in Section 3.7. The results of the interim analysis will not be shared with the investigators prior to the completion of the trial. Subject-level unblinding will be restricted to the unblinded statistician and unblinded statistical programmer performing the interim analysis, as well as designated unblinded Sponsor personnel who will review safety data at the subject level. Group summaries will be reviewed by the Sponsor's trial team in order to make scientific decisions for future studies.

3.3 Hypotheses/Estimation

Objectives of the study are stated in Section 3 of the protocol.

3.4 Analysis Endpoints

Immunogenicity and safety endpoints are listed below.

3.4.1 Immunogenicity Endpoints

The key immunogenicity endpoints include the following, in recipients of V114-SC, V114-IM and PCV13-SC:

- (1) Anti-PnPs serotype-specific IgG response rates [proportion of participants meeting serotype-specific IgG threshold value of $\geq 0.35 \mu\text{g/mL}$ measured by the pneumococcal electrochemiluminescence (PnECL) assay] at 1 month PD3 for the 15 serotypes contained in V114.
- (2) Anti-PnPs serotype-specific IgG GMCs for the 15 serotypes contained in V114, based on the serotype-specific IgG responses as measured by the PnECL assay at 1 month PD3.
- (3) The proportion of participants meeting threshold values at 1 month PD3 for diphtheria toxin ($\geq 0.1 \text{ IU/mL}$), tetanus toxin ($\geq 0.01 \text{ IU/mL}$), pertussis toxin ($\geq 10 \text{ EU/mL}$), pertussis FHA ($\geq 10 \text{ EU/mL}$) as well as polio virus types 1 [neutralizing antibody titers (NA) $\geq 1:8$], 2 (NA $\geq 1:8$) and 3 (NA $\geq 1:8$).

The same measures at pre Dose 4 and 1 month PD4, as well as geometric mean titers (GMTs) of diphtheria, tetanus, acellular pertussis, inactivated polio vaccine (DTaP-IPV) at 1 month PD3, pre Dose 4 and 1 month PD4 will also be analyzed.

3.4.2 Safety Endpoints

Refer to Section 4.2.1.2 of the protocol for the description of the safety measurements in this trial.

3.5 Analysis Populations

3.5.1 Immunogenicity Analysis Populations

The PP population will serve as the primary population for the analysis of immunogenicity data in this trial. The PP population consists of those participants who are not considered protocol violators.

Potential deviations that may result in the exclusion of a participant from the PP population for all immunogenicity analyses (serotype-specific IgG and DTaP-IPV at 1 month PD3, pre-dose 4 and 1 month PD4) include:

- Failure to complete vaccination of V114 or PCV13 at Doses 1 through 3 with correct clinical material and route of administration as per the randomization schedule and according to the protocol-specified visit window (refer to Section 1.3 of the protocol).
- Receipt of prohibited medication or prohibited vaccine prior to study vaccination at Dose 1, 2 or 3

Additional potential deviations that may result in the exclusion of a participant from the PP population for specific immunogenicity analyses (depending on the time point or endpoint for analysis) include:

- Failure to receive V114 or PCV13 at Dose 4 with correct clinical material and route of administration as per the randomization schedule and according to the protocol-specified visit window: this will result in the exclusion from all PP analyses (serotype-specific IgG and DTaP-IPV) at 1 month PD4.
- Failure to complete vaccination of DTaP-IPV at Doses 1 through 3 according to the protocol-specified visit window: this will result in the exclusion from the PP analysis of DTaP-IPV at all timepoints.
- Failure to receive DTaP-IPV at Dose 4 according to the protocol-specified visit window: this will result in the exclusion from PP analysis of DTaP-IPV at 1 month PD4.
- Receipt of prohibited medication or prohibited vaccine prior to a blood sample collection: the impact on the analysis of immunogenicity data will be assessed on a case-by-case basis.
- Collection of blood sample at the time point for the analysis outside of the pre-specified window, or lack of valid serology results: this will result in the exclusion from the PP analysis for particular timepoint(s) and/or endpoint(s) whose valid results are not available.

The final determination on protocol violations for 1 month PD3 analysis will be made prior to the database lock at 1 month PD3 for the interim analysis and will be documented in a separate memo. Protocol violators at Pre-dose 4 and 1 month PD4 will be identified prior to the final database lock at 1 month PD4.

The full analysis set (FAS) population will also be used for supplementary analysis of the key immunogenicity endpoints. The FAS population consists of all randomized participants who received at least one vaccination and have at least one serology result. Participants will be included in the vaccination group to which they are randomized for the analysis of immunogenicity data.

3.5.2 Safety Analysis Population

The APaT population will be used for the analysis of safety data in this trial. The APaT population consists of all randomized participants who received at least one dose of trial vaccine. Participants will be included in the group corresponding to the clinical material and route of administration they actually received for the analysis of safety data using the APaT population. For most participants this will be the group to which they are randomized. Participants who receive incorrect clinical material or whose route of administration is incorrect will be included in the group as outlined below:

- Participants who receive the same clinical material (V114 or PCV13) with the same route of administration throughout the trial will be considered belonging to the group corresponding to the clinical material and route of administration.
- Participants whose clinical materials (V114 and PCV13) and/or route of administration are partially different among the vaccinations will be summarized separately from any of the 3 vaccination groups.
- Incorrect route of administration for DTaP-IPV will not alter the vaccination group for safety analysis; the group will be determined based on the clinical material and route of administration for V114 or PCV13 only.

3.6 Statistical Methods

The results from all possible pairwise comparisons (V114-SC vs. PCV13-SC, V114-IM vs. PCV13-SC, V114-SC vs. V114-IM) will be presented for those analyses which involve calculations of between-group differences.

3.6.1 Statistical Methods for Immunogenicity Analyses

The immunogenicity analyses will be conducted for each serotype separately.

The proportion of participants with IgG concentrations $\geq 0.35 \mu\text{g/mL}$ at 1 month PD3 will be summarized by vaccination group. Within-group 95% CIs will be calculated based on the method of Clopper and Pearson. The between-group differences, along with the corresponding 95% CIs based on the method of Miettinen and Nurminen, will be calculated. The proportion of participants meeting threshold values at 1 month PD3 for diphtheria toxin, tetanus toxin, pertussis toxin, pertussis FHA as well as polio virus types 1, 2 and 3 will be analyzed in the same fashion. The data (serotype-specific IgGs as well as diphtheria toxin, tetanus toxin, pertussis toxin, pertussis FHA as well as polio virus types 1, 2 and 3) obtained at pre Dose 4 and 1 month PD4 will also be analysed in the same fashion.

The IgG concentrations at 1 month PD3 will be natural log transformed and analyzed using an ANOVA model with a factor for vaccination group. The within-group means and the between-group mean differences, along with the corresponding 95% CIs, will be estimated using this model. The point estimates as well as the lower and upper limits of the 95% CIs will be exponentiated to obtain the estimates on the original scale for IgG GMCs by vaccination group and IgG GMC ratios. The serotype-specific IgG concentrations obtained at pre Dose 4 and 1 month PD4, as well as the antibody titers for diphtheria toxin, tetanus toxin, pertussis toxin, pertussis FHA and polio virus types 1, 2 and 3 obtained at 1 month PD3, pre Dose 4 and 1 month PD4 will be analyzed in the same fashion.

The same analysis will also be performed for IgG (proportion of participants concentrations $\geq 0.35 \mu\text{g/mL}$ and GMC) in subjects whose baseline IgG were $< 0.35 \mu\text{g/mL}$.

For concentration or titer measurements that are smaller than the lower bound of the assay detectable range, half of the lower bound will be used for analyses.

Reverse cumulative distribution curves will be drawn by serotype and timepoint.

Table 1 summarizes immunogenicity analyses.

Table 1 Analysis Strategy for Immunogenicity Variables

Endpoint / Variable (Description, Time Point)	Statistical Method [†]	Analysis Population	Missing Data Approach
Secondary objective #1			
Proportion of participants with serotype-specific IgG $\geq 0.35 \mu\text{g/mL}$ at 1 month PD 3	Miettinen and Nurminen	PP (Primary) FAS (Supportive)	Missing data will not be imputed
Secondary objective #2			
Serotype-specific IgG GMCs at 1 month PD3	ANOVA [‡]	PP (Primary) FAS (Supportive)	Missing data will not be imputed
Secondary objective #3			
Proportion of participants meeting threshold values for diphtheria toxin, tetanus toxin, pertussis toxin, pertussis FHA as well as polio virus types 1, 2 and 3 at 1 month PD3	Miettinen and Nurminen	PP (Primary) FAS (Supportive)	Missing data will not be imputed
Tertiary/Exploratory Objective #1			
Proportion of participants with serotype-specific IgG $\geq 0.35 \mu\text{g/mL}$ at:	Miettinen and Nurminen	PP	Missing data will not be imputed
• Pre Dose 4 • 1 month PD4			
Tertiary/Exploratory Objective #2			
Serotype-specific IgG GMCs at:	ANOVA [‡]	PP	Missing data will not be imputed
• Pre Dose 4 • 1 month PD4			
Tertiary/Exploratory Objective #3			
Proportion of participants meeting threshold values for diphtheria toxin, tetanus toxin, pertussis toxin, pertussis FHA as well as polio virus types 1, 2 and 3 at:	Miettinen and Nurminen	PP	Missing data will not be imputed
• Pre Dose 4 • 1 month PD4			
Tertiary/Exploratory Objective #4			
GMTs for diphtheria toxin, tetanus toxin, pertussis toxin, pertussis FHA as well as polio virus types 1, 2 and 3 at:	ANOVA [‡]	PP	Missing data will not be imputed
• 1 month PD3 • Pre Dose 4 • 1 month PD4			
[†] Statistical models are described in further detail below:			
[‡] ANOVA model with natural log-transformed antibody responses as response variable and vaccination group as a single factor			
IgG = immunoglobulin G, PD = post-dose, GMC = geometric mean concentration, PP = per-protocol, FAS = full analysis set, ANOVA = analysis of variance, FHA = filamentous hemagglutinin			

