Nonstudy Pediatric Vaccines	(X)	(X)	(X)	(X)	(X)	(X)	Injectable vaccines should not be administrated in the same limb as the study vaccine.
Provide Vaccination Report Card (VRC)	X	X	X		X		See Section 8.1.9 for details.
VRC Collection		X	X	X		X	
Review VRC data		X	X	X		X	
Immunogenicity Procedures							
Collect Blood Samples for IgG Immunogenicity Assays	X*			X	X*	X	*Prior to vaccination
Collect Blood Samples for DTaP-IPV Immunogenicity Assays				X	X*	X	*Prior to vaccination

Study Period	Screening						Notes
	Intervention						
Visit Number	Visit 1	Visit 2	Visit 3	Visit 4	Visit 5	Visit 6	
Standard Age/ Scheduled Time	3 months	4 months	5 months	1 month PD 3	12~15 months	1 month PD 4	The age of the subject will fall within the appropriate age range for each trial visit.
	DOSE 1	DOSE 2	DOSE 3	POST DOSE 3	DOSE 4	POST DOSE 4	
Visit Window	3 months of age to 1 day prior to 4months of age	28 to 42 days after Visit 1	28 to 42 days after Visit 2	28 to 42 days after Visit 3	12 months of age to 1 day prior to 16 months of age	28 to 42 days after Visit 5	Months of age is calculated according to the participant's birth date.
Safety Procedures							
Full Physical Examination	X						To be performed by the investigator before vaccination to check inclusion/exclusion criteria/eligibility.
Targeted Physical Examination		X	X		X		To be performed by the investigator before vaccination.
Weight	X						
Body Temperature Measurement	X	X	X		X		Pre-vaccination body temperatures measured by site staff. (See section 8.3.2 for details)
30 Minutes Post Vaccination Observation Period	X	X	X		X		Subjects will be observed after study vaccination by blinded study personnel only.
AE Monitoring	←=====→						Nonserious AEs are to be reported from Days 1 through 14 following each vaccination. SAEs and deaths are to be reported throughout the duration of an individual's study participation.
Future Biomedical Research							
Collect Buccal Swabs for Future Biomedical Research	X						Collected from randomized participants who provided consent for FBR (Section 8.8)

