2 INTRODUCTION

Merck Sharp & Dohme Corp. (MSD) is developing an investigational 15-valent pneumococcal conjugate vaccine (PCV) (referred to as V114) for the prevention of pneumococcal disease (PD) caused by the serotypes in the vaccine. V114 contains the 13 serotypes (1, 3, 4, 5, 6A, 6B, 7F, 9V, 14, 18C, 19A, 19F, 23F) present in the licensed vaccine PCV13 (pneumococcal 13-valent conjugate vaccine [diphtheria CRM₁₉₇ protein], Wyeth Pharmaceuticals, a subsidiary of Pfizer, Inc., Philadelphia, PA), plus 2 additional serotypes (22F, 33F).

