3 HYPOTHESES, OBJECTIVES, AND ENDPOINTS

There is no formal hypothesis testing in this study.

The following objectives and endpoints will be assessed in healthy Japanese infants 3 months of age.

Primary Objectives	Primary Endpoints

Objective: To describe the safety and tolerability profiles of V114 given subcutaneously (V114-SC) and V114 given intramuscularly (V114-IM) in healthy infants.	
Solicited injection-site adverse events (AEs) during Day 1 to Day 14 postvaccinationSolicited systemic AEs during Day 1 to Day 14 postvaccinationVaccine-related serious adverse events (SAEs) during Day 1 to 1 month post-Dose 4 (PD4)
Secondary Objectives	Secondary Endpoints

Objective: To assess the anti-pneumococcal polysaccharide (PnPs) serotype-specific Immunoglobulin G (IgG) response rates (proportion of participants meeting serotype-specific IgG threshold value of $\geq 0.35 \mu\text{g/mL}$) at 1 month post-Dose 3 (PD3) for each vaccination group.	
Anti-PnPs serotype-specific IgG responses for the 15 serotypes contained in V114 at 1 month PD3

Objective: To assess the anti-PnPs serotype-specific IgG Geometric Mean Concentrations (GMCs) at 1 month PD3 for each vaccination group.	
Anti-PnPs serotype-specific IgG responses for the 15 serotypes contained in V114 at 1 month PD3

Objective: To assess the proportion of participants meeting threshold values* for protective responses to DTaP-IPV (Diphtheria toxin, Tetanus toxin, Pertussis toxin, Pertussis filamentous hemagglutinin (FHA) and Polio virus type 1/2/3) at 1 month PD3 for each vaccination group. 
Threshold value*: Diphtheria toxin level ≥ 0.1 IU/mL, Pertussis PT level ≥ 10 EU/mL, Pertussis FHA level ≥ 10 EU/mL, Tetanus toxin level ≥ 0.01 IU/mL, Neutralizing antibody titers (NA) of Polio virus type 1/2/3 $\geq 1:8$
	
The antibody responses for DTaP-IPV at 1 month PD3
Tertiary/Exploratory Objectives	Tertiary/Exploratory Endpoints

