4.2.1 Rationale for Endpoints

4.2.1.1 Immunogenicity Endpoints

Serotype-specific IgG

Sera from participants will be used to measure vaccine-induced serotype-specific IgG for all 15 serotypes (1, 3, 4, 5, 6A, 6B, 7F, 9V, 14, 18C, 19A, 19F, 22F, 23, and 33F) included in V114 using the pneumococcal electrochemiluminescence (PnECL) assay. Anti-PnPs serotype-specific IgG responses will be measured at baseline, 1 month PD3 for infant series (primary series), pre-Dose 4 for toddler (booster) to evaluate the anamnestic antibody responses and the persistence of protective immunity and 1 month PD4 for booster to measure the responses after Dose 4.

Immunogenicity endpoints for the comparison of PCVs in children are based on IgG antibodies responses. Such responses are consistent with the recommendations from the World Health Organization (WHO) and many regulatory agencies worldwide and include serotype-specific measurements of the following endpoints: a) the proportion of subjects achieving IgG antibody concentrations ≥ 0.35 $\mu\text{g/mL}$ 4 weeks after third dose; and b) the IgG GMCs measured 4 weeks after the third and fourth doses.

Immunogenicity of DTaP-IPV

For the objectives, the immunogenicity endpoint is the proportion of subjects meeting threshold values for protective responses to diphtheria toxin, pertussis toxin, pertussis FHA, tetanus toxin, and polio virus type 1/2/3 at 1 month PD3, pre-Dose 4 and 1month PD4. The infection control threshold levels of responses to DTaP-IPV are defined as shown in [Table 1](#) based on the WHO [World Health Organization 2017-1] [World Health Organization 2017-2], Japanese infection survey [Ministry of Health, Labor and Welfare., et al 2013] and clinical findings [Plotkin SA. 2010][Kato T.1990].

Table 1 Threshold levels of protective responses to DTaP-IPV

DTaP-IPV	Diphtheria Toxin	Tetanus Toxin	Pertussis Toxin	Pertussis FHA	Polio Type 1	Polio Type 2	Polio Type 3
Infection control threshold level	≥ 0.1 IU/mL	≥ 0.01 IU/mL	≥ 10 EU/mL	≥ 10 EU/mL	NA $\geq 1:8$	NA $\geq 1:8$	NA $\geq 1:8$

FHA: filamentous hemagglutinin, NA: Neutralizing antibody titers (dilution)

In addition, the endpoints also include evaluation of the GMTs for components of DTaP-IPV measured at 1 month PD3, pre-Dose 4 and 1 month PD4.

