3.6.3 Summaries of Demographics and Baseline Characteristics

The comparability of the vaccination groups for each relevant demographic and baseline characteristic will be assessed by the use of summary tables. No statistical hypothesis tests will be performed on these characteristics. The number and percentage of subjects randomized and vaccinated, and the reasons for discontinuation, will be displayed by group. Demographic variables, prior and concomitant therapies and vaccines will be summarized by group.

The proportion of participants with serotype-specific IgG concentrations at baseline above the lower bound of the assay detectable range will be summarized by vaccination group.

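### PD3 IgG GMC ratios ignore the collected pre-Dose 1 IgG: a supportive ANCOVA could narrow them for the 13 shared serotypes, while 22F and 33F need a V114-only fit for correct coverage

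*Combined protocol and SAP*

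**What the plan says.** Protocol 9.6.1 (Table 4) and sSAP 3.6.1 (Table 1) use the same model for IgG GMCs and GMC ratios: an "ANOVA model with natural log-transformed antibody responses as response variable and vaccination group as a single factor". Each serotype is modelled separately, and sSAP 3.6 applies one set of contrasts to all: "The results from all possible pairwise comparisons (V114-SC vs. PCV13-SC, V114-IM vs. PCV13-SC, V114-SC vs. V114-IM) will be presented". The secondary objective is framed by group: "To assess the anti-PnPs serotype-specific IgG Geometric Mean Concentrations (GMCs) at 1 month PD3 for each vaccination group".

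Baseline IgG will exist. Protocol 4.2.1.1 says "Anti-PnPs serotype-specific IgG responses will be measured at baseline, 1 month PD3 for infant series (primary series"), and the row "Collect Blood Samples for IgG Immunogenicity Assays" in the Schedule of Activities marks Visit 1, before vaccination. The DTaP-IPV row has no Visit 1 sample, so the point concerns IgG only.

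The sSAP uses baseline IgG in two ways: it repeats the IgG analyses in infants whose baseline was below 0.35 µg/mL (3.6.1), and it summarises by group the proportion with detectable baseline IgG (3.6.3). Two other provisions might display it without naming it: "Reverse cumulative distribution curves will be drawn by serotype and timepoint" (3.6.1) and "The comparability of the vaccination groups for each relevant demographic and baseline characteristic will be assessed by the use of summary tables" (3.6.3).

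Randomisation is unstratified (protocol 6.3.2), and 36 infants per arm are expected in the PD3 per-protocol population (sSAP 3.9). V114 has the 13 PCV13 serotypes "plus 2 additional serotypes (22F, 33F").

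**The concern.** The plan calls itself an estimation study, so the width and coverage of the intervals are what a reader takes from the GMC ratios. The project team sees PD3 group summaries at the interim when deciding about later studies. The pre-Dose 1 value of the same antibody is an obvious covariate, and no full-sample ratio uses it. The analysis in infants below 0.35 µg/mL restricts the sample rather than adjusting the full-sample ratio, and the other provisions only describe.

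For 22F and 33F there is a second issue. PCV13-SC infants are not vaccinated against these serotypes, so neither the slope on baseline nor the spread of ln IgG at PD3 need match the V114 arms. The three-arm ANOVA nevertheless uses one residual variance for every contrast, including V114-SC versus V114-IM, and the choice of route is one of the reasons for the trial (protocol 4.2).

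**Working it through.** **Plan's own figures.** The documents state no GMC-ratio precision, SD or correlation. The nearest figures are the nine intervals for differences in proportions at 36 per arm (sSAP Table 4). All nine reproduce to 0.1 point with the Miettinen–Nurminen score method, for example 31 versus 31: ±17.2%.

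**Inputs.** n = 36 per arm and 95% two-sided intervals (sSAP 3.9, 3.6.1). Assumed: normal ln IgG, the ln-SD, and the baseline-to-PD3 correlation r.

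**13 shared serotypes, equal SD and equal r in all arms.**

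- ANOVA half-width = t(105) × SD × √(2/36). At SD 1.0: 1.983 × 0.2357 = 0.467, so the interval is the ratio multiplied or divided by 1.60 (1.45 at SD 0.8, 1.75 at SD 1.2).
- ANCOVA width ÷ ANOVA width = [t(104)/t(105)] × √(1 − r²) × √(1 + 1/103) = 1.005 × √(1 − r²).
- The ratio is 1.005 at r = 0; 1.000 at |r| = 0.1; 0.985 at 0.2; 0.959 at 0.3; 0.921 at 0.4; 0.870 at 0.5. At SD 1.0 the factor 1.60 becomes 1.57 at 0.3 and 1.50 at 0.5.

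Three things reduce the gain:

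- *Missing baselines.* With m infants per arm left in the ANCOVA, the ratio is multiplied by about √(36/m). At |r| = 0.3 and three missing per arm: 0.959 × √(36/33) = 1.00. Break-even is at 1–2 missing per arm for |r| = 0.2, and about 3, 6 and 9 for 0.3, 0.4 and 0.5.
- *Values at the assay floor.* If half the baseline values were below range (assumed), the 4.1% gain at 0.3 falls to about 3% in simulation.
- *Different correlations between arms.* With −0.3, −0.3 and +0.3 in V114-SC, V114-IM and PCV13-SC (assumed), a common slope gains nothing in simulation.

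**22F and 33F, V114-SC versus V114-IM.** Let the V114 ln-SD be 1.0 and the PCV13-SC ln-SD be s (assumed).

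- The pooled SD is √((1 + 1 + s²)/3): 0.887, 0.938 and 1.109 for s = 0.6, 0.8 and 1.3.
- The true SD for this contrast is 1.0, so pooled coverage is about 2Φ(1.983 × pooled SD) − 1 = 92.1%, 93.7% and 97.2%. Simulation gives about 92%, 93.5% and 97%; fits in the two V114 arms, adjusted or not, hold 95%.
- Two-arm ANCOVA width ÷ pooled ANOVA width = 1.995 × √(1 − r²) × √(1 + 1/68) ÷ (1.983 × pooled SD). At r = 0.3 the numerator is 1.995 × 0.954 × 1.007 = 1.917.

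| PCV13-SC ln-SD (assumed) | Pooled ANOVA coverage | Two-arm ANCOVA width against pooled ANOVA, r = 0.3 |
|---|---|---|
| 0.6 | about 92% | 9% wider |
| 0.8 | about 93.5% | 3% wider |
| 1.0 | 95% | 3% narrower |
| 1.3 | about 97% | 13% narrower |

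At s = 0.6 and r = 0 the two-arm ANCOVA is 14% wider. Where the two-arm interval is wider, that is because the pooled one is too short.

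**The case against.** The strongest reply is that this is a preference. The ANOVA already delivers the secondary objective, the GMC in each group. There is no hypothesis or margin, the correlation is unknown, and at |r| of 0.2 or less the gain is negligible and can be lost to one or two missing baselines per arm. The sponsor has also considered baseline IgG and chose a restricted analysis. Most of this stands, and it keeps the point optional. It does not remove it: the restricted analysis answers a different question, the covariate is already collected, and the cost under equal correlation and SD is 0.5% if the correlation is zero.

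Two stronger readings should be resisted. A reader might infer that the single-factor ANOVA is biased or an error because baseline is left out. The documents do not support that: allocation is randomised, so for the shared serotypes the unadjusted ratio is unbiased and only precision is in question. A reader might also infer that a V114-only ANCOVA for 22F and 33F must narrow the interval, or cost at most about 1%. The second figure (1.2% wider at r = 0) holds only with equal SDs in all arms, which is doubtful for serotypes that PCV13 lacks; no fixed worst case can be stated.

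**Conclusion.** The point holds as an optional improvement in two parts. For the 13 shared serotypes, a supportive baseline-adjusted ratio could narrow the interval by about 4% at |r| = 0.3 and 13% at 0.5, with nothing gained near 0.1. These sizes assume equal SD and correlation across arms and few missing baselines. For 22F and 33F the case for a separate fit is coverage, not precision: the pooled three-arm interval for V114-SC versus V114-IM is at its nominal level only if the PCV13-SC spread matches that of the V114 arms. The size and direction of any departure rest on assumed SDs, so the documents do not show that undercoverage will occur.

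**What to change.** In the sSAP, before the PD3 interim database lock:

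- *13 shared serotypes.* Add a supportive per-protocol ANCOVA on ln PD3 IgG with vaccination group and ln baseline IgG of the same serotype, and apply the existing half-of-lower-bound rule to baseline values. Use it for GMC ratios only. The ANOVA stays the main analysis and the source of within-group GMCs, and its ratio stands if the two differ. Infants without a baseline value leave the ANCOVA only; report their number by group.
- *22F and 33F.* Estimate V114-SC versus V114-IM from the two V114 arms alone, unadjusted, with the baseline-adjusted version as supportive. State that the pooled three-arm interval does not govern this contrast. The unadjusted ratio itself does not change; only its interval does. Add no adjusted ratio against PCV13-SC for these two serotypes.
- Report baseline IgG GMCs by group and keep the analysis in infants below 0.35 µg/mL.
- If the PD3 lock has passed, label the ANCOVA post hoc.

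The cost is sSAP wording, 15 supportive models with 41 adjusted ratios (13 × 3 + 2 × 1), two unadjusted two-arm fits and one baseline table. No new sample is needed. The downsides are infants lost from the adjusted model, little or no gain where correlation is weak or differs between arms, and a second set of ratios without multiplicity adjustment.
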